4. **Vital Signs, Weight, and Height:** Vital signs will be measured at Screening, predose, and 2 hours ( $\pm 1$  hour) post-dose at Study Injection Visits during the Treatment Cycle 1 (Days 0 and 14), Treatment Cycle 2 (Days 60 and 74), and Treatment Cycle 3 (Days 120 and 134). Vital signs will also be measured at Study Visits on Days 30, 84, 144, and 180/ET (Day 180 or Early Termination). After the Participant has rested in the seated position for 5 minutes, vital signs will be collected, including temperature, sitting blood pressure, heart rate, respiratory rate, and oxygen saturation on room air. The method of temperature measurement should be according to the Site's policy and should be consistently applied. Weight will be collected at Screening and predose at Study Injection Visits (Days 0, 14, 60, 74, 120, and 134); height will only be measured at Screening.
5. **Complete Physical Examination** will be performed at Screening, predose on Days 0, 14, 60, 74, 120, and 134, and at Study Visits on Days 30, 84, 144, and 180/ET. The examination will include the following: head, eyes, ears, nose, and throat (HEENT); heart; lungs; abdomen; extremities; lymph nodes; neurological; musculoskeletal system; and skin/integumentary systems. Any abnormalities should be categorized as clinically significant (CS) or not clinically significant (NCS), and the abnormalities should be recorded as adverse events, except at Screening.
6. **12-Lead Electrocardiogram (ECG)** will be performed at Screening, Day 84, and Day 180/ET. Any clinically significant findings at Screening will be recorded as part of the medical history. Clinically significant abnormalities are to be recorded as adverse events, except at Screening. The ECG recording must be stored with the Participant's records.
7. **Coagulation Profile** will be evaluated at Screening and will include prothrombin time (PT), partial prothrombin time (PTT), and International Normalized Ratio (INR).

---

**8. Serum Chemistry and Hematology:** Laboratory assessments will be evaluated at Screening (to establish eligibility) and on Days 60, 120, and 180/ET.

**Chemistry** includes sodium, potassium, chloride, bicarbonate, calcium, inorganic phosphate, magnesium, glucose, amylase, lipase, creatine kinase, lactate dehydrogenase, and:

- a. Kidney function tests (blood urea nitrogen, creatinine)

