- b. Liver function tests (aspartate aminotransferase [AST], alanine aminotransferase [ALT], alkaline phosphatase, gamma-glutamyl transpeptidase [GGT], total bilirubin, total protein, and albumin)

**Hematology** includes platelet count, hemoglobin, hematocrit, white blood cell count, and neutrophil count

**9. Blood Sample for Future Genetic Testing:** A blood sample will be collected at predose on Day 0 and stored.

**10. Viral Screening** is to be conducted at Screening and includes tests for human immunodeficiency virus (HTV), human T cell lymphotropic virus (HTLV) I/II antibody with reflex confirmatory assay, hepatitis B virus (HBV: IgM HBcAb, HBsAb, and HBsAg, and a quantitative HBV if needed clinically), and anti-hepatitis C virus (HCV) antibodies and a positive qualitative PCR if needed clinically. Testing will be performed at a local laboratory. All tests for HIV, HTLV, HBV, and HCV must be completed and negative prior to randomization.

**11. Urine Pregnancy Test:** Women of childbearing potential must have a negative urine pregnancy test at Screening, predose at Study Injection Visit on Day 0 and Day180/ET.

**12. Slow Vital Capacity (SVC)** will be measured at Screening, predose on Days 0, 60, and 120, and at Study Visits on Days 30, 84, 144, and 180/ET.

**13. Concomitant Medications and Procedures:** Record all medications or vaccines, including over-the-counter or prescription medicines, vitamins, herbal supplements, and procedures that the Participant was receiving during the 30 days prior to completion of the informed consent process at Screening, predose at Study Injection Visits on Days 0, 14, 60, 74, 120, and 134, and at Study Visits on Days 30, 84, 144, and 180/ET. For each medication, treatment, or procedure, the following information will be collected: Medication trade or generic name, type of procedure, indication, start date, stop date or ongoing, dose, units, frequency, and route.

**14. Randomization:** Completion of Screening activities, randomization, and first Study Injections (Treatment Cycle 1, Day 0) will occur on the same day (Day 0).

**15. Study Injections:** IM injections of Engensis or Placebo will be administered during Treatment Cycle 1 (1st and 2nd Study Injections on Days 0 and 14), Treatment Cycle 2 (3rd and 4th Study Injections on Days 60 and 74), and Treatment Cycle 3 (5th and 6th Study Injections on Days 120 and 134).

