6. ATLIS
7. Pregnancy test (Day 0 only)
8. Complete physical examination
9. SVC (predose Day 0, 60, and 120)
10. ALSAQ-40 (predose on Day 0)
11. Blood draw for serum chemistry, and hematology (predose on Days 60 and 120)
12. Muscle biopsy (predose on Day 0)

A summary of the schedule of evaluations and Visits during the study can be found in the [SoA](#).

#### 4.1.1.1. Treatment Cycle 1

Participants will receive Engensis or Placebo by IM injections to the right and left sides of the specified muscles on Days 0 and 14 as shown in [Table 1](#).

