### 5.1. Inclusion Criteria

1. Male or female Participants age  $\geq$  18 years, but  $\leq$  80 years, at time of completion of the informed consent process
2. Clinically definite or probable Amyotrophic Lateral Sclerosis (ALS) or laboratory-supported probable ALS as defined in the revised El Escorial/Airlie House diagnostic criteria
3. The site of onset of ALS symptoms is a limb and experiencing symptoms of lower motor dysfunction (e.g., weakness, atrophy, cramps, poor circulation, etc.) with upper motor neuron symptoms (e.g., brisk reflexes, spasticity)
4. Onset of ALS symptoms  $\leq$  4 years
5. Slow Vital Capacity (SVC)  $\geq$  50% of predicted value at Screening
6. Not taking riluzole, or on a stable dose (defined as no noted toxicities) for at least 30 days prior to Screening and throughout the study
7. Not taking edaravone or on a maintenance cycle for at least 30 days prior to Screening and throughout the study
8. For females of childbearing potential, a negative urine pregnancy test at Screening and on Day 0
9. Male Participants and their female partners must agree to use double-barrier contraception during the study or provide proof of postmenopausal state (minimum 1 year) or surgical sterility
10. Male Participants must not donate sperm during the study
11. Female Participants must be nonpregnant, nonlactating, and either postmenopausal for at least 1 year, or surgically sterile for at least 3 months, or agree to use double-barrier contraception from 28 days prior to randomization (Day 0) and/or their last confirmed menstrual period prior to study randomization (whichever is longer) until the end of the study
12. Capable of complying and willing to comply with the requirements and restrictions in the informed consent form and this protocol
13. Willing to forgo new experimental ALS treatments for at least 6 months following randomization

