### **8.5.8. Pregnancy and Contraception**

#### **8.5.8.1. Pregnancy Test (Women of Childbearing Potential Only) and Contraception**

Female Participants must be nonpregnant, nonlactating, and either postmenopausal for at least 1 year, or surgically sterile for at least 3 months, or agree to use double-barrier contraception from 14 days prior to randomization and/or their last confirmed menstrual period prior to study randomization (whichever is longer) until 2 months after the last visit on Day 180.

Double-barrier contraception may include, but is not limited to, intrauterine device with spermicide, female condom with spermicide, diaphragm with spermicide, cervical cap with spermicide; having a male sexual partner who agrees to use a male condom with spermicide; or having a sterile sexual partner.

For women of childbearing potential, a urine beta human chorionic gonadotropin ( $\beta$ -HCG) test will be performed during Screening and before randomization (Day 0); results of the test must be negative. The  $\beta$ -HCG test will also be performed at Day 180/ET to evaluate whether the Participant is pregnant.

The rhythm method is not considered acceptable method of contraception.

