#### **8.5.8.2. Pregnancy**

The Investigator will collect pregnancy information on any female Participant who becomes pregnant while participating in this study. The initial information will be submitted to the Sponsor within 24 hours of learning of a Participant’s pregnancy.

---

Further dosing will be discontinued for any female Participant who becomes pregnant during the study.

The Participant will be followed to determine the outcome of the pregnancy. The Investigator will collect follow-up information on the Participant and the neonate, and the information will be forwarded to the Sponsor. Generally, follow-up will not be required for longer than 6 to 8 weeks beyond the estimated delivery date.

While pregnancy itself is not considered to be an AE or SAE, any pregnancy complication or elective termination of a pregnancy for medical reasons will be reported as an AE or SAE. A spontaneous abortion (occurring at < 22 weeks gestational age) or stillbirth (occurring at > 22 weeks gestational age) is always considered to be an SAE and will be reported as such. Other abnormal pregnancy outcomes (e.g., fetal death, congenital anomalies, ectopic pregnancy) are also considered SAEs and will be reported.

Any post-study pregnancy-related SAE considered possibly, probably, or definitely related to the study drug by the Investigator will be reported to the Sponsor. While the Investigator is not obligated to actively seek this information in former study Participants, he or she may learn of an SAE through voluntary reporting.

The Investigator will record a narrative description of the course of each pregnancy and its outcome.

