Measured values of serum chemistry and hematology analyses and their changes from baseline, will be presented with descriptive statistics at each visit by treatment group (Tables 14.3.4.1 and 14.3.4.3). Incidence of clinically significant values and shift tables by the clinical significance based on laboratory assessments will be presented for each parameter (Tables 14.3.1.9, 14.3.4.2, 14.3.4.4). Percentages for each parameter will be based on the number of participants who have at least one measurement for at baseline and at corresponding post-baseline visit.

Result of urine pregnancy test is variable with two possible values: positive / negative. The test should be performed only for women with childbearing potential at Screening, Day 0 pre-dose and End of Study. Urinalysis will be presented only in a listing.

Results of serum chemistry, hematology and urine pregnancy tests will be listed (Listings 16.2.8.1 – 16.2.8.3).

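### No pregnancy test is scheduled between Day 0 and Day 180, so no scheduled test can trigger the stop-dosing rule before the five later injection days

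*Protocol*

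**What the plan says.** The test times are the same wherever they are given.

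- Protocol Section 1.3, footnote 11: "Women of childbearing potential must have a negative urine pregnancy test at Screening, predose at Study Injection Visit on Day 0 and Day180/ET". The corresponding row of the schedule agrees.
- Protocol Section 4.1.1 lists the assessments before the first injections of each cycle (Days 0, 60 and 120). Item 7 restricts the test to the first of these: "Pregnancy test (Day 0 only)".
- Protocol Section 8.5.8.1: the urine test "test will be performed during Screening and before randomization (Day 0); results of the test must be negative". It adds that the "test will also be performed at Day 180/ET to evaluate whether the Participant is pregnant".
- SAP Section 6.14.2: "The test should be performed only for women with childbearing potential at Screening, Day 0 pre-dose and End of Study".

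The rule that depends on detection is in Protocol Section 8.5.8.2: "Further dosing will be discontinued for any female Participant who becomes pregnant during the study".

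There are other safeguards. Under inclusion criterion 11, women who are neither postmenopausal nor surgically sterile must "agree to use double-barrier contraception from 28 days prior to randomization (Day 0)". Under footnote 5, a complete physical examination "will be performed at Screening, predose on Days 0, 14, 60, 74, 120, and 134". Weight and adverse events are also recorded before each injection.

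**The concern.** A rule that stops dosing on pregnancy protects a participant only if the pregnancy is found while doses remain. After Day 0, the only scheduled tests are at Day 180 or at early termination. The first comes after all dosing is over, and the second when the participant is already leaving. For five of the six injection visits the rule therefore depends on the participant recognising and reporting a pregnancy, or on someone ordering an unscheduled test.

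What is at stake is avoidable exposure to a gene therapy product in circumstances where the protocol itself says dosing must stop. There is a smaller consequence for the safety data, which are the primary objective. Section 8.5.8.2 always counts a spontaneous abortion as a serious adverse event, and one that occurs in an unrecognised pregnancy could go unreported.

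**Working it through.** The plan gives no figure of its own to reproduce. The check compares test days with injection days.

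**Inputs.** Injections are given on Days 0, 14, 60, 74, 120 and 134, with 128 injections (32 mg VM202 in the Engensis arm) per visit, 768 injections and 192 mg in total (Protocol Section 4.4.2). Tests from Day 0 onward are on Day 0 predose and Day 180/ET. All days are nominal.

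**Visits without a test.** Days 14, 60, 74, 120 and 134, which is 5 of 6. They carry 5 × 128 = 640 injections and 5 × 32 = 160 mg (640/768 = 83.3%).

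**Intervals now.** Longest gap between tests: 180 − 0 = 180 days. Longest time from the latest test to an injection: 134 − 0 = 134 days. Last injection to next test: 180 − 134 = 46 days.

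**Doses given after an unrecognised pregnancy becomes detectable (Engensis arm).** Injections = visits remaining × 128, and mg = visits remaining × 32. The last column assumes predose tests on Days 60 and 120.

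| Becomes detectable | Current schedule | With tests on Days 60 and 120 |
|---|---|---|
| After the Day 0 test, before Day 14 | 5 visits, 640 injections, 160 mg | 1 visit, 128 injections, 32 mg |
| Between Days 14 and 60 | 4 visits, 512, 128 mg | 0 |
| Between Days 60 and 74 | 3 visits, 384, 96 mg | 1 visit, 128, 32 mg |
| Between Days 74 and 120 | 2 visits, 256, 64 mg | 0 |
| Between Days 120 and 134 | 1 visit, 128, 32 mg | 1 visit, 128, 32 mg |
| After Day 134 | 0 | 0 |

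A placebo participant receives the injections but no VM202.

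**Intervals with the added tests.** Longest gap between tests: 60 days. Longest time from test to injection: 14 − 0 = 74 − 60 = 134 − 120 = 14 days.

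**Sensitivity to the clock.** The table counts from when a test could turn positive. Counting from the start of pregnancy, there is a lag before detection, which the documents do not give. A pregnancy begun just before Day 0 and missed that day could receive all 6 visits now (768 injections, 192 mg). With the added tests, a pregnancy begun just before Day 60 and missed that day receives Days 60 and 74: 2 × 128 = 256 injections, 64 mg. Two visits is the maximum for any assumed lag shorter than 46 days (60 − 14 = 120 − 74 = 46).

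**The case against.** The strongest reply is that this is a deliberate and consistent choice. Five places agree, one of them explicitly limits the test to Day 0, and the stop-dosing rule still works on self-report or an unscheduled test. The largest exposure requires a detectable pregnancy to go unnoticed from Day 14 to Day 134, about 120 days, through predose adverse event recording, weights and repeated complete examinations. Contraception is required, and Section 8.5.8.1 extends it to two months after Day 180. Section 4.4 describes very limited systemic distribution and a circulating half-life of 2 to 5 minutes, so the maternal milligrams above are not fetal exposure. The number of women at risk may be zero. Parts of the nonclinical and risk text are redacted, and the Investigator's Brochure and the contraceptive guidance named in Section 10.4.2 are not among the documents reviewed, so a rationale may exist out of view.

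Much of this stands as context. The probability is low and cannot be estimated, and the worst case is an upper bound. It does not remove the gap. Contraception lowers the chance of pregnancy but does not detect it. The listed examination has no pregnancy-specific element, and Section 8.5.2 prefers open-ended, non-leading questions about adverse events. With limited distribution already described, the protocol still requires dosing to stop. An unseen rationale might justify accepting the risk, but it would not supply a test before the later injections.

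A fair criticism of the remedy is that testing on Days 60 and 120 leaves Days 14, 74 and 134 without a test of their own. That is a judgement of proportion: each of those visits would then follow a negative test by nominally 14 days.

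**Conclusion.** The concern holds. No scheduled test can trigger the stop-dosing rule before any of the five injection days after Day 0. The worst case after detectability is 640 of 768 injections and 160 of 192 mg. It assumes an Engensis participant, full dosing at nominal visits, a pregnancy detectable before Day 14, and no recognition or report by other means.

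How many participants this could affect cannot be calculated, because the number of women of childbearing potential among the 18 is not given. This is a participant-safety weakness with low probability and potentially serious consequences. No endpoint, sample size or analysis result depends on it. The change is recommended because the gap undercuts the protocol's own rule and is cheap to narrow.

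**What to change.** For women of childbearing potential, add a predose urine pregnancy test on Days 60 and 120, with a negative result required before any injection. Change the text in four places:

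1. Protocol Section 1.3, schedule row and footnote 11: test at Screening and predose on Days 0, 60 and 120, negative before injection; repeat at Day 180/ET.
2. Protocol Section 4.1.1, item 7 of the predose list: Days 0, 60 and 120.
3. Protocol Section 8.5.8.1: add the two test days and the requirement for a negative result.
4. SAP Section 6.14.2: add Day 60 and Day 120 predose to the test times.

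The visit order in the schedule footnotes already puts the pregnancy test before the physical examination and needs no change.

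The cost is two kits per woman tested, at most 2 × 18 = 36 even if every participant qualified. Both days are existing visits with predose blood sampling, so no visit or staff is added. The rest is a short amendment with ethics review, any consent form update the board requires, a small data-capture change, and a slight burden on the women tested.

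If the sponsor prefers a test before every later injection (Days 14, 60, 74, 120 and 134), no injection visit is left untested and the longest gap between tests is 46 days, for at most 5 × 18 = 90 kits. If the sponsor keeps the present schedule, the protocol should state why.

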**FOOTNOTES FOR THE SCHEDULE OF ACTIVITIES**

**Note:** The Schedule of Activities includes activities during Screening and all Study Visits.

**Order of Assessments during Visits (if assessment is to be performed):** AEs/TEAEs, vital signs and weight, ALSFRS-R, HHD, ATLIS, pregnancy test, complete physical exam, SVC, ALSAQ-40, other questionnaires (PGIC and CGIC), blood sample collection for laboratory assessments, and muscle biopsy

- a Day 0 is the Baseline Visit
- b The Day 14 Visit will be scheduled 13-15 days after the Day 0 Visit, the Day 74 Visit will be scheduled 13-15 days after the Day 60 Visit, and the Day 134 Visit will be scheduled 13-15 days after the Day 120 Visit
- c Muscle biopsies will be collected as the last procedure of the Visit. It is collected predose on Day 0.
- d Day 84 muscle biopsy is optional.

**Abbreviations:** AEs = adverse events; AESI = adverse events of special interest; ALSFRS-R = Revised Amyotrophic Lateral Sclerosis Functional Rating Scale; ALSAQ-40 = Amyotrophic Lateral Sclerosis Assessment Questionnaire, 40 questions; ATLIS = accurate test of limb isometric strength; CGIC = Clinical Global Impression of Change; D = day; ET = early termination or withdrawal; HHD = Handheld Dynamometry; PGIC = Patient Global Impression of Change; SVC = Slow Vital Capacity; TEAEs = treatment-emergent adverse events; TESAEs = treatment-emergent serious adverse events

1. **Informed Consent** process is to be completed at Screening prior to conducting any study-specific procedures.
2. **Demographics and Baseline Characteristics** will include age, gender, race, and ethnicity and will be collected at Screening.
3. **Medical History and Familial Cancer History:** A medical history and familial cancer history will be obtained at Screening. The Investigator will confirm the diagnosis of ALS using the revised El Escorial / Airlie House diagnostic criteria. Participants will be confirmed as having clinically definite ALS, clinically probable ALS, or clinically probable laboratory-supported ALS  $\leq 4$  years.

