**16. Revised Amyotrophic Lateral Sclerosis Functional Rating Scale (ALSFRS-R)** will be performed at the Clinical Site at Screening, predose on the Days 0, 60, and 120, and on Days 30, 84, 144, and 180/ET.

**17. Handheld Dynamometry (HHD)** will be measured at the Clinical Site predose on Days 0, 60, and 120, and at Visits on Days 30, 84, 144, and 180/ET.

**18. ATLIS** will be measured (only at sites that have the ATLIS equipment) predose on Days 0, 60, and 120, and at Visits on Days 30, 84, 144, and 180/ET.

**19. Amyotrophic Lateral Sclerosis Assessment Questionnaire, 40 questions (ALSAQ-40)** will be measured predose on Day 0 and at Visits on Days 84 and 180/ET.

**20. Patient Global Impression of Change (PGIC) and Clinical Global Impression of Change (CGIC)** will be conducted at Visits on Days 84 and 180/ET.

**21. Muscle Biopsy:** Biopsies of the gastrocnemius muscle around the injection sites will be collected and stored at Day 0 predose, and Days 84 (optional) and 144 (approximately10 days after the second day of injections of Treatment Cycles 2 and 3).

---

22. **Adverse Events (AEs), Treatment-Emergent Adverse Events (TEAEs), Serious Adverse Events (SAEs) and Treatment-Emergent Serious Adverse Events (TESAEs):** AEs will be recorded after informed consent until the first injections on Day 0. After the start of the 1st Injections on Day 0 through Day 180, AEs will be recorded as treatment-emergent adverse events (TEAEs). Treatment-emergent serious adverse events (TESAEs) occurring after randomization and throughout the study will be recorded. SAEs occurring after the completion of the consent process and before the 1st Injections on Day 0 should be recorded and reported as SAEs only if associated with a protocol-specified procedure. All SAEs, and TESAEs occurring after the time of the 1st Injections through the last Study Visit on Day 180, should be recorded and reported to the Sponsor/designee within 24 hours of awareness of the SAE/TESAE by the Site.

23. **Adverse Events of Special Interest (AESIs):** All AESIs will be continuously monitored throughout the study.

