#### **8.5.4.3. Injection Site Reactions**

The most common ISRs in the prior Phase 1/2 study in ALS Participants were local pain and bruising at the site of injection. A follow-up notification for ISRs will occur within 2 to 3 days after each Study Injection Visit. The location and temporal relationship to the most recent injections will determine whether the event is an ISR and should be reported as a TEAE. For an AE to qualify as an ISR, the reaction must be located in close proximity to an injection site and be first observed and graded within 48 hours following Study Injections. ISRs that remain unresolved after 48 hours will continue to be assessed at subsequent Visits as ongoing AEs until resolved.

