#### **10.1.11. Insurance**

Matters relating to insurance for this study are to be defined in the agreement between the Sponsor and the institution.

**10.2. Appendix 2. Adverse Events: Definitions and Procedures for Recording, Evaluating, Follow-up, and Reporting****10.2.1. Definition of AE****AE Definition**

- An AE/TEAE is any untoward medical occurrence associated with the use of an investigational product or study procedure in a clinical study Participant, whether or not considered related to the study intervention.
- NOTE: An AE/TEAE can therefore be any unfavorable and unintended sign (including an abnormal laboratory finding), symptom, or disease (new or exacerbated) temporally associated with the use of study intervention or procedure.

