#### 10.4.2. Definitions

Active Infection	Chronic infection or severe active infection that may compromise the Participant's wellbeing or participation in the study, in the Investigator's judgment
Day 14, etc.	Day 14 (for example) refers specifically to the actual day of the Visit designated as the Day 14 Visit, and not to the 14 th day of the study for a Participant.
End of Study	Completion of the last Visit or procedure shown in the Schedule of Activities for the last Participant remaining in the study

Highly Effective Contraception Method	See Contraceptive Guidance
Injection Site Reaction	An AE located in close proximity to the injection sites on the target muscles and first observed within 48 hr following Study Injections
Investigator	The PI or appropriate study site personnel whom the PI designates to perform a certain duty
Placebo	Placebo comprises 45 mg sodium chloride and 55 mg sucrose in 5 mL water for injection. Engensis vials contain the same excipients.
Safety Analysis Population	All Participants who receive at least one Study Injection
Sponsor	Helixmith Co., Ltd. and its representatives contracted to provide services for study conduct
Study Drug	Engensis or Placebo
Study Injection	Injection of Engensis or Placebo
Participant	Anyone who is consented for Screening
Treatment Arm	The group of Participants assigned to receive Study Drug or the group assigned to receive Placebo during the first 6 months of treatment
Treatment Cycle	Two sets of Study Injections 14 days apart comprising a single dose
VM202	The active pharmaceutical ingredient of Engensis: a novel genomic complementary deoxyribonucleic acid (cDNA) hybrid human hepatocyte growth factor (HGF) coding sequence (HGF-X7) expressing two isoforms of HGF, HGF 728 and HGF 723

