6.2.9 Compliance

Compliance will be calculated as $100\% * [\text{volume of administered injections}] / [\text{volume of planned injections}]$. Volumes of planned injections are:

- Each anatomic area for dosing day:
 - Abductor pollicis brevis, right: 1 mL
 - 2 Abductor pollicis brevis, left: 1 mL
 - 3 First dorsal interosseous, right: 1 mL
 - 4 First dorsal interosseous, left: 1 mL
 - 5 Biceps, right: 4 mL
 - 6 Biceps, left: 4 mL

QMD Ref: Worldwide-TMP-ST-005-7.0 Effective: 12Aug2019	Governing QMD: Worldwide-SOP-ST-001
Confidentiality Statement	

This document is the property of Worldwide Clinical Trials Inc. and may not be duplicated, copied, altered or removed from company without prior approval from Worldwide Quality Assurance or in compliance with Worldwide Standard Operating Procedures.

Worldwide Clinical Trials Controlled Quality Management Document			
 WORLDWIDE CLINICAL TRIALS	Sponsor:	Helixmith Co., Ltd.	
	Protocol Number:	VMALS-002-2	
STATISTICAL ANALYSIS PLAN VERSION 3.0			

- 7 Deltoid, right: 4 mL
- 8 Deltoid, left: 4 mL
- 9 Extensor carpi radialis, right: 1 mL
- 10 Extensor carpi radialis, left: 1 mL
- 11 Flexor carpi ulnaris, right: 1 mL
- 12 Flexor carpi ulnaris, left: 1 mL
- 13 Flexor carpi radialis, right: 1 mL
- 14 Flexor carpi radialis, left: 1 mL
- 15 Quadriceps, right: 10 mL
- 16 Quadriceps, left: 10 mL
- 17 Gastrocnemius, right: 6 mL
- 18 Gastrocnemius, left: 6 mL
- 19 Tibialis anterior, right: 6 mL
- 20 Tibialis anterior, left: 6 mL
- Each side for each dosing day: 32 mL
- Each dosing day: 64 mL
- Each anatomic area for treatment cycle:
 - Abductor pollicis brevis, right: 2 mL
 - 2 Abductor pollicis brevis, left: 2 mL
 - 3 First dorsal interosseous, right: 2 mL
 - 4 First dorsal interosseous, left: 2 mL
 - 5 Biceps, right: 8 mL
 - 6 Biceps, left: 8 mL
 - 7 Deltoid, right: 8 mL
 - 8 Deltoid, left: 8 mL
 - 9 Extensor carpi radialis, right: 2 mL
 - 10 Extensor carpi radialis, left: 2 mL
 - 11 Flexor carpi ulnaris, right: 2 mL
 - 12 Flexor carpi ulnaris, left: 2 mL
 - 13 Flexor carpi radialis, right: 2 mL
 - 14 Flexor carpi radialis, left: 2 mL
 - 15 Quadriceps, right: 20 mL
 - 16 Quadriceps, left: 20 mL
 - 17 Gastrocnemius, right: 12 mL

QMD Ref: Worldwide-TMP-ST-005-7.0 Effective: 12Aug2019	Governing QMD: Worldwide-SOP-ST-001
Confidentiality Statement	

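### A reaction at the Day 0 calf biopsy wound, first seen within 48 hours after the injections, counts as an injection site reaction in a primary endpoint

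*Protocol*

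**What the plan says.** **Biopsy.** Footnote 21 of the Schedule of Activities (protocol 1.3) states: "Biopsies of the gastrocnemius muscle around the injection sites will be collected and stored at Day 0 predose". Footnote c makes the biopsy the last procedure of a visit but adds an exception: "It is collected predose on Day 0". In protocol 4.1.1 it is the twelfth and last item on the list of assessments that come directly before the injections. Only the Day 84 biopsy is optional.

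**Injections.** The biopsied muscle is also a target muscle. Protocol Table 1 gives 12 gastrocnemius injections per side on Day 0. SAP 6.2.9 agrees: "Gastrocnemius, right: 6 mL" at 0.5 mL per injection is 12 injections.

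**ISR definition.** Protocol 8.5.4.3 says: "The location and temporal relationship to the most recent injections will determine whether the event is an ISR". It then requires that "the reaction must be located in close proximity to an injection site and be first observed and graded within 48 hours following Study Injections". Appendix 4 (10.4.2) defines an ISR as "An AE located in close proximity to the injection sites on the target muscles and first observed within 48 hr following Study Injections". Neither text has a causality element or an exclusion for biopsy wounds.

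**Adverse events and grading.** Protocol 10.2.1 defines an adverse event as "any untoward medical occurrence associated with the use of an investigational product or study procedure", so a reaction to the biopsy is an adverse event. Appendix 3 grades pain, skin reactions and bruising, swelling or bleeding, taking the most severe on each limb after each treatment. Footnote 24 has the worst reaction recorded.

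**Endpoint.** ISR incidence, Engensis against Placebo, is one of the primary endpoints (protocol 9.3.1, SAP 3.1). The SAP plans one incidence table (14.3.1.8) and one listing (16.2.7.4). It has no rule for events at the biopsy site.

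**The concern.** A muscle biopsy can cause pain, bruising, swelling and bleeding, which the ISR scale also grades. On Day 0 the wound lies around the injection sites and is made shortly before the injections. A wound reaction that first shows itself afterwards passes both parts of the ISR test.

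Three things are at stake:

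- **Incidence.** Some participants may be counted as having an ISR when the only reaction came from the biopsy.
- **Contrast.** If this happens at a similar rate in both arms, both incidences rise and the difference between them shrinks. In a safety trial that is the unreassuring direction, because a local excess on Engensis becomes harder to see.
- **Grade.** The most severe finding on a leg sets the grade, so a biopsy haematoma can displace a milder injection reaction on that leg. If only the worst reaction is captured, the displaced one cannot be recovered at analysis.

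**Working it through.** The plan states no ISR rate, and the sample size of 18 (12:6) is given without a power calculation, so there is no figure to reproduce. The check is of the definition first and of possible size second.

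**Step 1: which biopsies and reactions qualify.**

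- Day 0: the biopsy precedes the injections on the same day. A reaction first observed within 48 hours after the injections qualifies. One already noted before the first injection does not, because it was not first observed afterwards.
- Days 84 and 144: these visits fall nominally 84 - 74 = 10 and 144 - 134 = 10 days after the latest injections, outside the 48-hour window.
- So one of the six injection visits is exposed.

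**Step 2: effect on incidence.** Let p be the true participant-level ISR incidence over the whole study. Let b be the share of participants with a biopsy-wound reaction that meets the ISR definition. Assume b is equal in both arms and independent of true ISRs. Then:

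- observed incidence = p + (1 - p) × b
- observed risk difference = (pE - pP) × (1 - b), where pE and pP are the true incidences on Engensis and Placebo

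The factor (1 - p) reflects that a biopsy reaction changes a participant's status only if there is no other ISR at any visit.

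**Step 3: numbers.** No value of b is in the documents; 10%, 30% and 50% are assumptions. The first row takes p = 4%, the upper end of the 1-4% injection-site pain reported for earlier Engensis studies (protocol 2.2), described there as similar on placebo. The other p values are assumptions.

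| True p, Engensis vs Placebo | b = 10% | b = 30% | b = 50% |
|---|---|---|---|
| 4% vs 4% | 13.6% vs 13.6% | 32.8% vs 32.8% | 52.0% vs 52.0% |
| 30% vs 10% | 37% vs 19% | 51% vs 37% | 65% vs 55% |
| 95% vs 90% | 95.5% vs 91.0% | 96.5% vs 93.0% | 97.5% vs 95.0% |

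For example, 0.30 + 0.70 × 0.10 = 0.37 and 0.10 + 0.90 × 0.10 = 0.19. In the middle row the risk difference falls from 20 points to 18, 14 and 10, and the risk ratio from 3.0 to 1.95, 1.38 and 1.18.

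**Step 4: small numbers.** One reclassified Placebo participant moves that arm by 1/6, about 17 points. The chance of at least one biopsy-wound reaction among the 6 is 1 - (1 - b)^6: 47%, 88% and 98% at b = 10%, 30% and 50%. It changes the arm's incidence only if that participant has no other ISR.

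**The case against.** The strongest reply is that the plan already has ways to tell the two kinds of reaction apart. Footnote 24 asks about reactions at injection sites, and a biopsy wound is not one. Protocol 10.2.5 asks for a diagnosis where possible and has the investigator weigh alternative causes. Appendix 3 grades each leg separately. The SAP tabulates ISRs by preferred term and lists them individually, and 18 participants can be read line by line. The biopsy and injection guidelines and the eCRF are not among the documents; they may already record the biopsied side.

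Much of this limits the problem, but none of it overrides the definition. Causality is assessed, yet ISR status does not depend on it. A biopsy-specific diagnosis may be recorded, but neither document requires one. Line review can separate events only if the biopsied side and the position of the reaction were captured.

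A second reply is that a location-and-time rule is objective and errs toward counting harm. Moving events out of the ISR count asks staff to attribute reactions in a muscle both biopsied and injected, and could remove true ISRs. That stands, and it is why the primary count should be left as defined.

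A reader might also infer that every wound reaction becomes an ISR, or that both arms are driven toward a ceiling. The documents do not support either. Reactions seen before injection are outside the definition, and no biopsy-reaction rate is given. The earlier ALS study reports 26 mild ISRs in 18 participants without saying how many were affected, so p is unknown too.

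**Conclusion.** The point holds in a limited form. As written, the ISR definition includes Day 0 biopsy-wound reactions first observed within 48 hours after the injections. They can raise incidence and the worst leg grade in both arms and dilute the contrast. Only the Day 0 visit is exposed, and incidence changes only in participants with no other ISR.

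The size cannot be worked out from the documents. Given equal b in both arms and independence from true ISRs, the risk difference shrinks by the factor (1 - b). The shift in an arm's incidence, (1 - p) × b, runs from 48 points (p = 4%, b = 50%) to near zero when almost everyone has a true ISR. Grades can be affected even then.

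It would be wrong to infer a false excess on Engensis: both arms have the same biopsy before any study drug, under double-blind conditions. Nor is a type I error at issue, since protocol 9.3.1 plans no formal testing of safety. The documents show that the count can be contaminated, not that it will be.

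**What to change.** Keep the biopsy and the primary ISR count as defined. Then:

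1. **eCRF.** Make sure the biopsied side is recorded, if it is not already. Flag Day 0 reactions at or next to the biopsy wound as possibly procedure-related, and record them separately from the worst injection-site reaction on that leg.
2. **Protocol 8.5.4.3.** Add a sentence describing the flag and stating that it does not change ISR status.
3. **SAP Table 14.3.1.8.** Add one ISR incidence row that excludes Day 0 reactions in the biopsied calf.

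The cost is one or two eCRF fields, a sentence and one table row. The separate recording has to be done at data capture, because a displaced milder reaction cannot be rebuilt later. The added row may drop some true ISRs, so it supplements the main count and does not replace it.
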